3.1 Selection and Study enrollment procedures

The study population will be identified from a random sample from the population register of men in the age group 50-60 (including age 60) years in the county of Göteborg and 10 surrounding municipalities: Ale, Alingsås, Herrljunga, Härryda, Kungälv, Lerum, Mölndal, Partille, Vårgårda, and Öckerö.

The extraction of the initial random study population will be carried out stratified on county, with respect to the number of inhabitants in that county.

3.2 Inclusion criteria

At date of randomization:

1. Alive
2. A registered address in the county of Gothenburg, Sweden or any of 10 specified surrounding municipalities
3. Age 50 to 60 years

3.3 Exclusion Criteria

At date of randomization:

1. A diagnosis of prostate cancer (will be excluded from analysis but will remain in the database (for future Ad Hoc analysis)
2. Emigration before randomization (date of emigration not updated in the Population Register at time of randomization)
3. Death before randomization (date of death not updated in the Population Register at time of randomization)

3.4 Randomization to Control Group and Screening Group

The Ethical committee at University of Gothenburg, working in accordance with Swedish rules and regulation, permits upfront randomization before consent. The first randomization, to control group and screening group, will be performed 1:1. Since January 2017, due to an observed lower than anticipated participation rate, the allocation was changed to 2:1 in order to reach a sufficient sample size in the SG to evaluate the primary objective at four years. The control group will be followed for prostate cancer incidence and prostate cancer mortality by cross-linking to the Regional Cancer registry as well as the Swedish Cause of death registry on the personal identification number, unique for each Swedish resident. The control group will thus constitute a pure control group receiving current clinical practice and standard care in Sweden today, which implies no regular organized PSA-testing (but opportunistic screening may occur). A mailed letter will inform men in the control group and that their participation is voluntarily (see 3.6 below).

When combining the men randomized with allocation ratio 1:1 up to January 22, 2017 with men randomized with ratio 1:2 thereafter, the distribution of follow-up times in the screening and control groups will differ. In order to achieve the same distribution of follow-up times in the two groups and hence make them comparable, only half of the men randomized to the control group up to January 22, 2017 will be considered. Therefore, a new variable called “active/non-active control group” was included in the database, where half of the men in the control group randomized up to January 22 2017 will be coded as “active”, the rest of the control men as “non-active”. The “active” men were randomly selected by taking year of birth and municipality into account, in the same way as they were balanced at randomization (see Amendment 4).

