3.5 Allocation of Screening Group to three study arms

Men randomized to the screening group and who accept participation will be randomly allocated 1:1:1 into one of the three study arms. Allocation to study arm will occur automatically and instantly the first time a man has a PSA test delivered to the central database. PSA test results are delivered electronically directly into the database from the central laboratory and there is no manual interference.

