6 STATISTICAL CONSIDERATIONS

6.1 Sample Size Calculation

The hypothesis is that the MRI-targeted biopsy only strategy would reduce insignificant cancer with 50%. Based on previous studies and expert knowledge, we assumed that the proportion of men diagnosed with insignificant cancer among men with PSA ≥ 3 in Arm 1 (reference arm) would be 9%. This gave a sample size of N=1,164 men with PSA ≥ 3 ng/mL to achieve 80% power, when having a two-sided test alternative and significance level 5%. Furthermore, we hypothesized that 7% among men attending PSA-screening would have an elevated PSA and that the participation rate would be 50%, which lead to the sample size N=33,260 altogether in the three screening-arms. Accounting for uncertainty in the hypothesized proportion of insignificant cancers and in the proportion of men with PSA ≥ 3

ng/mL among those screened, lead to the final sample size of N=36,000 for the SG. With an allocation rate of 1:2 between the CG and SG, altogether, N=54,000 men are needed to be included in the study.

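### The active/non-active definition in 3.4 gives no active code to controls randomised after January 22, 2017; this is probably a wording error, confined to the screening-versus-control comparison

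*Protocol*

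**What the plan says.** Section 3.4 of the protocol describes two allocation periods for the first randomisation: 1:1 between control group (CG) and SG up to January 22, 2017, and one control to two SG men after that. It recognises that pooling the periods would give the two groups different follow-up, and says that only one half of the early controls will be used. The purpose is explicit: "In order to achieve the same distribution of follow-up times in the two groups and hence make them comparable". It then defines the variable that carries this out: "half of the men in the control group randomized up to January 22 2017 will be coded as “active”, the rest of the control men" (this remainder gets the value non-active). The next sentence describes the active men as a random selection that takes year of birth and municipality into account. No sentence says how controls randomised after January 22, 2017 are coded.

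Section 6.1 gives the matching totals: "With an allocation rate of 1:2 between the CG and SG, altogether, N=54,000 men are needed to be included in the study", with 36,000 of these in the SG.

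In the table in 2.5, the CG enters Additional objective 2, the SG versus CG comparison of cancer-specific incidence and mortality, first assessed at 31 December 2027.

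**The concern.** The variable is named for the control group as a whole and has two values. Only a subset of the early controls is given the value active. Everyone else in the CG is then non-active, and in ordinary English that includes every man randomised to control after January 22, 2017. An analyst who selects active controls on this definition keeps no control from the 1:2 period, while the SG spans both periods. The follow-up imbalance that the variable was created to remove would then be produced by the variable itself, and the control group would be smaller than 6.1 implies.

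At stake is who counts as a control for the third of the three research questions in section 2, whether screening with pre-biopsy MRI reduces prostate cancer mortality relative to men who are not invited.

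**Working it through.** **Inputs.**
- SG size S = 36,000, total 54,000, CG:SG = 1:2 (6.1).
- CG:SG = 1:1 up to January 22, 2017 and 1:2 after (3.4), taken as holding exactly in each period.
- f = share of the SG randomised up to that date. The protocol does not give it; 0.10 to 0.90 is an assumed range.

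**Step 1. The plan's own figure.** 36,000 × 1.5 = 54,000, as stated. The implied CG is 54,000 − 36,000 = 18,000.

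**Step 2. Controls by period.**
- Early controls (1:1): f × 36,000.
- Later controls (1:2): (1 − f) × 36,000 / 2 = (1 − f) × 18,000.

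**Step 3. Active controls under the literal rule.** Half of the early controls and nobody else: f × 36,000 / 2 = f × 18,000.

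**Step 4. Active controls if all later controls are also active.** f × 18,000 + (1 − f) × 18,000 = 18,000, whatever f is.

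| f | Early controls | Later controls | Active, literal rule | SG : active, literal | Later entrants in SG | Later entrants among active, literal | Active, later controls kept |
|---|---|---|---|---|---|---|---|
| 0.10 | 3,600 | 16,200 | 1,800 | 20:1 | 90% | 0% | 18,000 |
| 0.25 | 9,000 | 13,500 | 4,500 | 8:1 | 75% | 0% | 18,000 |
| 0.50 | 18,000 | 9,000 | 9,000 | 4:1 | 50% | 0% | 18,000 |
| 0.75 | 27,000 | 4,500 | 13,500 | 2.67:1 | 25% | 0% | 18,000 |
| 0.90 | 32,400 | 1,800 | 16,200 | 2.22:1 | 10% | 0% | 18,000 |

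**Step 5. Check against the stated aim.** With later controls kept, the early ratio of active controls to SG is (f × 18,000) : (f × 36,000) = 1:2, and the later ratio is ((1 − f) × 18,000) : ((1 − f) × 36,000) = 1:2. The share of later entrants is 1 − f in both groups. The entry-date distribution and the 1:2 ratio in 6.1 are therefore both met. Under the literal rule neither is met for any f below 1.

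**Step 6. The narrower reading.** If the remainder means only the unselected early controls, men randomised later are neither active nor non-active. A selection on active drops them, with the same counts as in Step 3; a selection that removes non-active men keeps them, as in Step 4. The definition does not say which applies.

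**The case against.** The best defence is context. The sentence before the definition limits early controls to one half and drops nobody else, and the definition is introduced as its consequence. The paragraph speaks of combining the two periods, which makes no sense if one period supplies no controls. The phrase about the remaining controls can fairly be taken to mean the other half of the early ones. Section 3.4 also refers to Amendment 4 for this variable, and the SG versus CG analysis has its own addendum; neither is shown here. Most of this stands: the intention was very probably to keep later controls. It does not rescue the wording, because on that reading the later controls still have no code.

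The defence also holds against several stronger conclusions that a reader might draw:

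- **That the mortality comparison loses a known amount of power.** The protocol contains no mortality power calculation. The 18,000 follows from the allocation ratio, in a section that sizes the detection of insignificant cancer. Neither the early-period count nor the control mortality risk is given.
- **That most of the control information is lost.** That is so only if f is below 0.50. At f = 0.75 or 0.90 the literal rule keeps 13,500 or 16,200 of 18,000.
- **That the result would be biased in favour of screening.** Longer control follow-up would raise crude cumulative event proportions in controls. This protocol does not specify a crude analysis, and a person-time or time-to-event method would take unequal follow-up into account.
- **That the database is wrong.** Section 3.4 speaks of the variable as already created. Nothing in the document shows how it was coded.
- **That 6.1 needs rewording too.** Its total reproduces exactly, and no change there is shown to be necessary.

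**Conclusion.** The concern holds as a defect of definition. As written, 3.4 either excludes all controls from the 1:2 period or leaves them uncoded, and so fails to secure the paragraph's own aim and the ratio in 6.1. It is probably a wording error rather than a design decision.

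The logical fault does not depend on f; its size does. A literal selection would leave f × 18,000 controls, from 1,800 to 16,200 over the assumed range, against 18,000 when later controls are kept. This rests on the allocation ratios having been achieved and on an SG of 36,000.

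The reach is limited to Additional objective 2. The primary and secondary comparisons (Arm 1 against Arms 2 and 3 combined, later Arm 1 against Arm 2) use SG men only and are unaffected. Claims about mortality power, or about the direction of bias in the final result, cannot be supported from this document.

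**What to change.** Replace the definition in 3.4 with one that codes every control: all controls randomised after January 22, 2017, together with the randomly selected half of those randomised up to that date, are active; only the unselected half of the earlier controls are non-active.

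Before the SG versus CG analysis, tabulate the existing database variable by period and confirm that active CG:SG is about 1:2 in each. Check that the addendum for Additional objective 2 uses the same definition.

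The cost is one sentence in the protocol and one cross-tabulation. No new data and no change to the sample size section are needed.

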3.5 Allocation of Screening Group to three study arms

Men randomized to the screening group and who accept participation will be randomly allocated 1:1:1 into one of the three study arms. Allocation to study arm will occur automatically and instantly the first time a man has a PSA test delivered to the central database. PSA test results are delivered electronically directly into the database from the central laboratory and there is no manual interference.

3.6 Study participant information and consent

The Regional Ethics Review Board at University of Gothenburg approved the Göteborg-2 trial in January 2015, registration number 890-14. All men randomized to the SG or CG receive detailed information about the study by postal mail, on its design, benefits and risks, contact details, and a reference link to the study website. The website also includes a link to the Swedish National Board of Health and Welfare’s written information about PSA-testing and its pros and cons. Men in both groups are informed that participation is voluntary and can be terminated at any time by a deliberate action of the participant (opt out procedure). Written informed consent is thus not requested from all participants in the main study but men who have a positive screening-test and are invited for prostate biopsy are asked to sign an informed consent where they permit study personal to take part of their medical records. Informed consent is also requested in some side studies.

Due to low participation rate following invitation reminders in screening round 2, invitation reminders are since February 27, 2019 only sent in the first screening round (see Amendment 7).

4 STUDY INTERVENTION

4.1 Intervention

Arm (1) (reference arm)

- Screen-negative: If the total-PSA level is “normal”, i.e. below the cut-off 3.0 ng/mL, no further testing or examination will be performed, but all men will be re-invited.
- Screen-positive: If the total-PSA level is “elevated” above the cut-off i.e. ≥ 3.0 ng/mL, the man will be invited for an MRI.

All men will be recommended standard biopsy, i.e., digital rectal exam followed by TRUS-guided 12-core standard prostate biopsy according to the screening protocol. These standard biopsies will be taken with both the urologist and subject blinded to the MRI result. After these standard biopsies, the study nurse will show the urologist the result from the MRI examination, and in case of suspicious lesion at MRI, 3-4 targeted* biopsies in each of these lesions will be performed in the same séance; 3 targeted biopsies if one of the systematic biopsies already hit the area, and 4 targeted biopsies if otherwise.

- Men in whom MRI for any reason is not achievable or the result is inconclusive will only undergo systematic biopsies

Arm (2) (first experimental arm)

- Screen-negative: If the total-PSA level is “normal”, i.e., below 3.0 ng/mL, no further testing or examination will be performed. The man will be re-invited for screening identical to Arm (1).
- Screen-positive: If the total-PSA level is “elevated” ≥ 3.0 ng/mL, he will be offered MRI.
 - If the MRI is positive (PI-RADS 3-4), only targeted* biopsies will be performed, i.e. 4 biopsy cores targeted against each suspicious lesion, but no systematic biopsies.
 - If the MRI is positive (PI-RADS 5), targeted* biopsies will be performed, i.e., 4 biopsy cores targeted against each suspicious lesion but also systematic biopsies. Changed 2018-10-15 (see amendment 5)
 - If the MRI is negative no biopsies will be performed.
 - If the MRI is negative and PSA ≥ 10 and PSA density (PSAD), ≥ 0.1 , systematic 12-core biopsies will be performed. PSA cut off changed 2016-03-01 from 20 to 10 ng/mL (see amendment 1).
 - Men in whom MRI for any reason is not achievable, or the MRI is technically inferior (for example in men with hip prosthesis), are invited for urological examination with digital rectal examination (DRE) and transrectal ultrasound

(TRUS). These men are included in the intention to screen analysis but not in the per protocol analysis (see 6.2.1).

Arm (3) (experimental arm II)

- Identical to arm (2) except that the PSA-cut off is lower, ≥ 1.8 ng/mL.

Men in Arm 2 and 3 with cancer diagnosed at targeted biopsies during screening round 1 are recommended completion with systematic biopsies 6-12 weeks after the first biopsy.

* Targeted biopsy = biopsy targeted against MRI positive areas (suspicious for cancer)

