6.2 Analysis plan for the primary and secondary endpoints

6.2.1 Primary objective (Detection of insignificant cancer)

- Hypothesis

The proportion of men with insignificant cancer detected by PSA testing with threshold 3 ng/mL, systematic biopsies and MRI-targeted biopsies (p_1) will be different from the proportion detected when omitting systematic biopsies (p_2):

H_0 (null hypothesis): $p_1 = p_2$

H_A (alternative hypothesis): $p_1 \neq p_2$

Although the hypothesis of the investigators is one-sided, that MRI-targeted biopsies only will lower the proportion, the test is two-sided to allow for a significant effect in both directions.

- Analysis populations

First assessment (after completion of screening round 1): All men in arm 1 will be compared to all men in arm 2 and 3 combined. However, for men in arm 3, cancers detected in men with PSA < 3 ng/mL will be ignored.

Later assessments: the analysis will compare all men in arm 1 with all men in arm 2.

The analyses will primarily be carried out according to the intention to treat (ITT) principle, which here means that all men will be included in the analysis and belong to the arm they were allocated to, irrespective of whether they completed the intended diagnostic pathway with MRI and biopsies or not.

Furthermore, per protocol analyses will be carried out including only men who strictly follow the protocol.

An additional analyses will compare men in arm 1 who underwent MRI followed by systematic and possible targeted biopsies (if MRI positive) with those in arm 2 and 3 who underwent MRI and also targeted biopsies but ignoring results from possible systematic biopsies if those were taken at the primary biopsy and the targeted biopsies were benign.

- Analysis

Outcome measure is the relative difference of the proportion of insignificant cancers detected in arms 2 and 3 combined vs arm 1 (the cancers detected in men with PSA below 3 ng/mL in arm 3 will be ignored). In later assessments only arm 1 and 2 will be included. The result will be presented as a point estimate with a two-sided 95% confidence interval, and a p-value of the hypothesis test. Significance testing will only be carried out for the first definition of insignificant cancer (Gleason grade 3+3). The score method will be used for testing and confidence intervals (27). A p-value below 5% will be considered statistically significant.

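### The protocol excludes men without a usable MRI from the per-protocol set in arms 2 and 3 but gives no matching rule for arm 1, so the compared groups may be selected differently

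*Protocol*

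**What the plan says.** Three places in the Protocol bear on who enters the per-protocol set.

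- **Section 4.1, arm 2.** The rule covers "Men in whom MRI for any reason is not achievable, or the MRI is technically inferior (for example in men with hip prosthesis" and similar cases. These men are sent for urological examination with DRE and TRUS, and the text adds, with a pointer to section 6.2.1: "These men are included in the intention to screen analysis but not in the per protocol analysis". Arm 3 inherits this by being "Identical to arm (2) except that the PSA-cut off is lower".
- **Section 4.1, arm 1.** "Men in whom MRI for any reason is not achievable or the result is inconclusive will only undergo systematic biopsies". Nothing is said about their place in the per-protocol set.
- **Section 6.2.1, analysis populations.** "The analyses will primarily be carried out according to the intention to treat (ITT) principle". In addition, "per protocol analyses will be carried out including only men who strictly follow the protocol". No MRI criterion and no denominator is given for that set.

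Section 6.2.1 also plans a further analysis. Its arm 1 side consists of "men in arm 1 who underwent MRI followed by systematic and possible targeted biopsies (if MRI positive"; its arm 2 and 3 side consists of men who had both MRI and targeted biopsies.

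**The concern.** Whether a man can have a usable MRI does not depend on the arm to which he was allocated. A hip prosthesis occurs equally often in all three. A per-protocol rule that uses this factor should therefore use it on both sides of the comparison. Here the exclusion is written for arms 2 and 3 only. An arm 1 man without MRI who has his systematic biopsies has done what section 4.1 prescribes, so on the plain meaning of section 6.2.1 he qualifies.

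The per-protocol contrast would then compare an arm 1 group that includes men with no MRI information and no targeted cores with a group from which such men were removed. If the denominator is all screened men, the shift has a direction. Screen-positive men, the only ones who can contribute a counted cancer, leave arms 2 and 3, while screen-negative men stay. That lowers the apparent detection of insignificant cancer in the experimental arms. Section 6.2.2 analyses significant cancer in the same way, so apparent detection of significant cancer in those arms would fall too.

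**Working it through.** **Plan's own figures.** Section 6.1 assumes 9% insignificant cancer among arm 1 men with PSA ≥ 3 ng/mL, a 50% reduction (to 4.5%), 7% of attenders with elevated PSA, and 50% participation. It needs 1,164 men with PSA ≥ 3 ng/mL for 80% power at two-sided 5%. A continuity-corrected comparison of two proportions at 1:2 gives 382 men in arm 1 and 1,146 in total, 1.5% below 1,164. The next step is 1,164/(0.07 × 0.50) = 33,257, against the stated 33,260. The 9%, 4.5% and 7% can therefore serve as inputs. The point itself does not depend on the sample size.

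**Assumptions not in the document.** Let *u* be the share of men with PSA ≥ 3 ng/mL without a usable MRI, taken as 2–10%. Let *r* be the yield of insignificant cancer from systematic biopsy in such arm 1 men, taken as 4.5–18%. Men with a usable MRI yield 9% in arm 1 and 4.5% in arms 2 and 3, so excluding the others from all arms gives 0.045/0.09 = 0.50.

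**Case A: denominator is all screened men, exclusion in arms 2 and 3 only, r = 9%.**

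- Arm 1: 0.07 × 0.09 = 0.0063.
- Arms 2 and 3: 0.07 × (1 − u) × 0.045 / (1 − 0.07u).
- Ratio: 0.50 × (1 − u)/(1 − 0.07u).

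| u | Arms 2 and 3 | Ratio |
|---|---|---|
| 2% | 0.003087/0.9986 = 0.00309 | 0.491 |
| 5% | 0.0029925/0.9965 = 0.00300 | 0.477 |
| 10% | 0.002835/0.9930 = 0.00285 | 0.453 |

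Letting *r* run over 4.5–18% widens this to about 0.41–0.50. The lower end is u = 10%, r = 18%: (0.0405/0.993)/0.099 = 0.412. The upper end is u = 2%, r = 4.5%: (0.0441/0.9986)/0.0891 = 0.496. The calculation ignores arm 3 men with PSA 1.8–2.99 ng/mL who lack a usable MRI. Their share is not given, their cancers are not counted, and removing them would offset the shift slightly.

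For significant cancer, if the affected arm 1 men have average yield, the same factor (1 − u)/(1 − 0.07u) multiplies whatever the true ratio is: 0.981, 0.953 and 0.906 at u = 2%, 5% and 10%.

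**Case B: denominator is men with PSA ≥ 3 ng/mL, exclusion in arms 2 and 3 only.**

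- Arm 1: (1 − u) × 0.09 + u × r. Arms 2 and 3: 0.045.
- u = 10%, r = 4.5%: arm 1 = 0.0855; ratio 0.526.
- u = 10%, r = 9%: arm 1 = 0.0900; ratio 0.500.
- u = 10%, r = 18%: arm 1 = 0.0990; ratio 0.455.
- u = 2%: the ratio runs from 0.505 (r = 4.5%) to 0.490 (r = 18%).

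In case B the direction depends on *r*, and nothing shifts if these men have the average yield. In case A the ratio falls even then. Section 6.2.1 describes the compared populations as all men in each arm, which points to case A, but it fixes no denominator for the per-protocol set.

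**The case against.** A reader might infer that the protocol deliberately keeps arm 1 men without MRI and that the per-protocol groups are therefore not comparable. The document does not support that. No sentence says these men are kept. Arm 2 men without a usable MRI also follow a prescribed route, yet they are removed with a pointer to section 6.2.1. Strict adherence may thus have been meant as completing the MRI pathway, and that reading would remove the arm 1 men too. The two bullets also describe somewhat different men: arm 1 speaks of an inconclusive result, arm 2 of a technically inferior examination. This part of the objection stands, and it limits the point to what the literal text permits.

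Three further arguments carry less weight.

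- **The detail may be left to the SAP.** It may, but the protocol itself fixes the exclusion for two of the three arms, and the section it points to contains nothing that would extend it to the third.
- **An MRI-matched comparison is already planned.** The additional analysis requires MRI on both sides, but limits arms 2 and 3 to men who also had targeted biopsies. Read literally, it drops MRI-negative men who were not biopsied, so it cannot replace a symmetric per-protocol set.
- **The men differ between the bullets.** MRI that is not achievable is common to both, and section 5.1 refers to men with a non-achievable or inconclusive MRI without distinguishing arms.

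**Conclusion.** The point holds as an asymmetry in the written rule: an explicit exclusion for arms 2 and 3, none for arm 1, and no criterion in section 6.2.1 to settle it. Two analysts could build different arm 1 sets from this text.

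The likely shift is small to moderate and rests on an assumed 2–10% without a usable MRI. A true ratio of 0.50 would become about 0.49–0.45 with all screened men as denominator and a 9% yield in the affected men, in favour of arms 2 and 3. With men with PSA ≥ 3 ng/mL as denominator it would become 0.455–0.526, depending on a yield assumed at 4.5–18%. These figures apply only if the arm 1 men are in fact kept.

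A reader might also infer that the trial's main result is biased. It is not affected: the primary analysis is by intention to treat and includes all men whether or not they completed the pathway. This is a minor correction to a supportive analysis.

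**What to change.** In sections 4.1 and 6.2.1, state one identical MRI criterion (not achievable, technically inferior or inconclusive) that excludes men from the per-protocol set in all three arms. State the per-protocol denominator. Report the number of men excluded by arm. The intention-to-treat analysis and the clinical pathways stay as they are.

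The cost is a sentence or two in each section and the loss of a few arm 1 men from a supportive analysis. Section 9.3.1 says that screening round 1 was completed in 2021. If round 1 has already been analysed, the symmetric set should be labelled a post hoc sensitivity analysis and shown beside the per-protocol result.
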